### **9.7.3 Comparative Analysis**

#### **9.7.3.1 Estimation of Vaccine Effectiveness**

Cox proportional hazards regression, yielding a hazard ratio (HR; 95%CI), accounting for censoring, changing incidence over time, and competing risks (Section 9.7.3.3) will be estimated for the defined periods: i.e. 0 to 14 days after D1, 15 after D1 until D2, 0 to 14 days after D2 and 15-90 days, 91-180 days, and  $\geq 181$  days after D2 in comparison with similar followed periods from time zero in the unvaccinated group.

This method will calculate a single vaccine effectiveness measure for each period of observation (assumed constant over those defined periods) in vaccinated versus unvaccinated groups. Crude vaccine effectiveness will be calculated for all the outcomes as 1 minus HR.

The assumption of proportionality of the survival curves in the vaccinated and unvaccinated groups will be evaluated.

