#### **9.1.1.4 Definition of Time Zero**

In studies of vaccinated versus unvaccinated persons, researchers must determine the appropriate time point at which to identify patients and begin follow-up. Aligning the evaluation of eligibility criteria, covariate assessment, exposure assignment, and beginning of follow-up (time zero) avoids selection bias and immortal person-time bias and addresses a well-defined study question [13].

Time zero is the time when the vaccination status is assigned; all eligibility criteria must be fulfilled at that point, and COVID outcomes must start to be counted at that point [14].

Time zero in the vaccinated group will be the date when the 1st dose of COVID-19 vaccine is administered (i.e. recorded). That date will be also used for the unvaccinated pairs as Time zero.

The aim of the **Main analysis** will be the estimation of the effectiveness  $\geq 15$  days after full vaccination series whether 1- or 2-doses regimens (and regardless of delayed completion of 2-dose vaccine series ,i.e. recorded dates will be accepted as real world data even though the time between doses are not fully adjusted to recommended intervals). Analysis will be performed by vaccine brand.

In order to properly observe the moment when the effect of the vaccination starts, the period between 1st Dose and 14 days after the 2nd dose will be divided and compared with unvaccinated patients. Thus, at least 5 cut-of periods will be identified along each patient's follow-up contribution:

- 1) Non-exposed period among Unvaccinated patients (Reference for Effectiveness estimation)

- 2) D1-induction time: up-to 14 days after 1st dose
- 3) D1-effectiveness: 15 days after 1st dose to 2nd dose
- 4) D2-induction time: up-to 14 days after 2nd dose
- 5) D2-effectiveness in the short run: 15-90 days after 2nd dose
- 6) D2-effectiveness in the medium run: 91-180 days after 2nd dose
- 7) D2-effectiveness in the long run:  $\geq 181$  days after 2nd dose

[figure not shown]

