## **9.2 Setting**

This study will be conducted in Spain where the 1st COVID-19 vaccine was included in public campaigns after approval by the European Commission from 21st December 2020. The eligibility criteria will change over time according to prioritised vaccination groups as follows in Figure 1:

Due to the potentially changing incidence of COVID-19 over time and prioritised vaccination groups, comparisons within the study periods and prioritised criteria will be established as much as possible.

According to the 1st prioritized groups (see Figure above), the **study period** will begin on the 21st of December 2020. The end of study period will be the last date of data received at the start of the data collection. Since the vaccines start to request the vaccination for young people (for example: Pfizer requested to the FDA to expand use of its Covid-19 vaccine to adolescents ages 12 to 15 on 9th April 2021), no age restriction will be applied for the source population.

No sex restriction will be applied.

In BIFAP, as per quality and quantity criteria for research, and in order to ensure precise anamnesis, only those clinical histories considered up-to-standard are included in pharmacoepidemiological studies.

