### 9.3.1 Exposure Assessment and Time At Risk

Data will be collected from BIFAP database with data from Spain (described in [Data Sources](#)).

**Inclusion criteria** to the Source population: up-to-standard,  $\geq 1$  year baseline information in January 2021 in BIFAP. The last date of filling all the inclusion criteria will be the inclusion date. No restriction to age or sex will be applied.

**Exclusion criteria:** Patients with prevalent COVID vaccinations or infections ever before (i.e. washout period) the inclusion criteria will be excluded.

**Stop date:** the last moment of the following criteria will define the stop date to contribution: covid-19 infection, death, loss to follow-up and end of study period (the last date available in the data source at data collection).

**Exposure assessment:** The 1st vaccination recorded after the inclusion date will be the time zero for patients included in the vaccinated group, as explained in section 'Definition of Time Zero' [9.1.1.4](#).

From the source population, 10 individuals unvaccinated on or before time zero of the vaccinated pair (10:1) will be randomly selected among those with similar birth cohort, sex and region (matched criteria). Patients included in the comparison group, may be vaccinated later during their follow-up period and then contribute to the vaccinated group (from the date of vaccine administration ahead; i.e. time zero for the vaccinated group).

\*Note: All individuals vaccinated during their follow-up contribution will be included in the vaccinated group. While, a random selection of the unvaccinated individuals will be included as unvaccinated group.

The date and type of vaccine administered will be collected from the **Table of Vaccine** from BIFAP data model. In particular, Covid-19 vaccinations will be ascertained from official covid-19 vaccination registries and provided by the regional governments. The coding system is not known yet. The feasibility analysis will include an evaluation of the coding type, whether or not vaccines are recorded according to standardised system or not. We expect that either ATC07 (J07????) or National Code (CNF [Código Nacional de

Farmacia]) specific for pharmaceuticals in Spain is available for all vaccines administered.

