For the vaccines currently available, those with a 2-dose regimen, the second dose must be administered 21/28 days after the 1st dose. In order to identify potential data **entry errors** (e.g., two vaccination records too closed or 3 doses recorded, may indicate double recording of the same vaccination) and cut-off points, a description of interval between doses will be performed beforehand.

Current vaccines are intended to give protection at least for 21 and 28 days after the 2nd dose, however the protection in the median-long run is unknown. Thus, in order to estimate the duration of the effectiveness, the follow-up period after 2nd dose will be divided as aforementioned.

The **follow-up** period will be the time between time zero and stop date.

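### For two-dose brands the secondary one-dose window has no upper limit, so people late for or without dose 2 can carry far more of its person-time than their number and may bias one-dose VE in either direction

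*Protocol*

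**What the plan says.** Protocol section 9.1.1.4 divides follow-up after dose 1 into periods, with the stated aim "In order to properly observe the moment when the effect of the vaccination starts". Its one-dose effectiveness period starts on day 15 after dose 1 and ends at dose 2. Section 9.7.3.1 carries the same cut points into the Cox model: "0 to 14 days after D1, 15 after D1 until D2, 0 to 14 days after D2 and 15-90 days", followed by two later periods. It estimates a single VE per period, taken as constant within it.

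Four other statements determine how long a person can stay in the one-dose period:

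- Section 9.3.1 gives the schedule for two-dose products: "the second dose must be administered 21/28 days after the" first. It does not say which interval belongs to which brand.
- Section 9.1.1.4 accepts second-dose dates as recorded, "regardless of delayed completion of 2-dose vaccine series".
- Section 9.3.1 lists the reasons for ending follow-up as "covid-19 infection, death, loss to follow-up and end of study period". An overdue or missing second dose is not among them.
- Section 9.2 sets the horizon: "The end of study period will be the last date of data received at the start of the data collection". Section 6 dates that start to the end of June 2021.

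The main analysis in section 9.1.1.4 is effectiveness from 15 days after the full series. The one-dose period is secondary to it.

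**The concern.** The one-dose period mixes two kinds of time: short waits for a scheduled second dose, and long stretches in people who are late or never return. The second kind can grow until data cut-off, while the first is fixed by the schedule at one or two weeks. One constant hazard ratio over the whole period averages the two, with weights that depend on the completion rate and the length of follow-up.

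If overdue people have a different hazard, or if one-dose protection changes over the following months, the estimate no longer answers the question that section 9.1.1.4 asks about the onset of effect. The weights also depend on the dose interval. Section 9.1.1.4 analyses by brand and section 9.1.1.5 plans head-to-head comparisons, so a brand contrast in one-dose VE could partly reflect different mixing. The design is also uneven: time after dose 2 is split at 90 and 180 days because duration is unknown, while time after dose 1 can run as long and is not split.

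**Working it through.** **Plan's own figure.** The protocol states no person-time, completion rate or VE for the one-dose window, so there is nothing to reproduce here. The probabilities in section 9.5 do not concern this window.

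**Inputs from the protocol.** Window start day 15; interval g = 21 or 28 days (9.3.1); general vaccination from 22 March 2021 (9.5); data to the end of June 2021 (6, 9.2). From 22 March to 30 June is 100 days.

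**Assumptions.** A fraction f of 2%, 5% or 10% never gets dose 2 and everyone else is on time. The days T available after dose 1 are uniform on 0 to 100.

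**Person-time.** Within-interval days are max(min(T, g) − 15, 0); overdue days are max(T − g, 0), contributed only by non-completers. Summed over T = 0 to 100:

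- g = 21: within-interval C = 495, overdue O = 3,160
- g = 28: C = 1,027, O = 2,628

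Overdue share s = f·O / (C + f·O).

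| f | g = 21 | g = 28 |
|---|---|---|
| 2% | 63.2/558.2 = 11.3% | 52.56/1,079.56 = 4.9% |
| 5% | 158/653 = 24.2% | 131.4/1,158.4 = 11.3% |
| 10% | 316/811 = 39.0% | 262.8/1,289.8 = 20.4% |

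**Sensitivity of the share.**

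- If everyone has the full 100 days, s = f(100 − g) / [(g − 15) + f(100 − g)]. For g = 21 this is 20.8%, 39.7% and 56.8%; for g = 28 it is 10.0%, 21.7% and 35.6%.
- Counting 7 or 14 on-time days instead of 6 or 13 lowers the largest main-scenario values from 39% to 35% and from 20% to 19%.
- If dose 2 is only delayed, to day 42, and 5% are late, all window time of the late group is 0.05·28 / (0.05·28 + 0.95·7) = 17.4% for g = 21. For g = 28 it is 1.4/14.7 = 9.5%.

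**Effect on VE.** At equal background incidence the pooled hazard ratio is roughly (1 − s)·HR within interval + s·HR overdue. Take 0.4 within interval (VE 60%). The hazard ratios are illustrative.

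| Overdue HR | g = 21, f = 2 / 5 / 10% | g = 28, f = 2 / 5 / 10% |
|---|---|---|
| 0.7 | VE 56.6 / 52.7 / 48.3% | VE 58.5 / 56.6 / 53.9% |
| 0.4 | VE 60% throughout | VE 60% throughout |
| 0.2 | VE 62.3 / 64.8 / 67.8% | VE 61.0 / 62.3 / 64.1% |

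The shift therefore runs from about 12 points down to about 8 points up, and is zero when the hazards agree. At the same 5% non-completion and an overdue HR of 0.7, the two intervals give 52.7% and 56.6%: a difference of about 4 points with no true difference between brands.

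**The case against.** The strongest case against has four parts.

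**The protocol already separates these people.** Section 9.7.2 treats on-time, partial and delayed completion as separate exposure groups compared with the unvaccinated. Section 9.3.1 will describe dose intervals beforehand, partly to find cut-off points, and the list of periods in 9.1.1.4 is worded as a minimum. These provisions are a good basis for a fix. But the strategy groups sit under the incidence analysis with a broken cross-reference, no cut-off is linked to the one-dose window, and 9.7.3.1 keeps that window whole.

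**Other safeguards apply.** Recipients of a second brand become switchers, infection ends follow-up, health-care use and frailty markers are updated adjustment candidates, and proportionality will be evaluated. Matched comparison over similar periods limits calendar-time bias. These reduce the problem. They do not remove unmeasured selection into non-completion, and a proportionality check has no defined window in which to report what it finds.

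**One dose until the second, at real-world intervals, is a legitimate quantity.** It is. But a single constant VE for it depends on follow-up length and completion, so it is hard to interpret as onset of effect or to compare across brands.

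**Bias is not shown.** This stands. A reader might infer that one-dose VE will be distorted, or biased downward, because a few people dominate the window. The documents do not support that: they give neither a non-completion rate nor these people's hazard, and person-time share alone biases nothing. Nor do they support extending the concern to the main estimate, which starts after the full series.

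**Conclusion.** The point holds as a weakness in a secondary analysis. The one-dose window is open-ended in both places that define it, no rule caps or splits it, and one constant VE is fitted. People late for or without dose 2 can therefore hold a share of person-time well above their number: about 11% to 39% for a 21-day gap and 5% to 20% for a 28-day gap, on assumed non-completion of 2% to 10% and up to 100 days of follow-up. Longer follow-up raises these shares; shorter follow-up or mere delay lowers them.

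Whether one-dose VE is biased, and in which direction, depends on hazards that the documents do not give. The fall from 60% to 48% is the most extreme cell of the main scenario for an overdue HR of 0.7, not an expected result. The change is worth making because it is cheap and settles the meaning of the estimate before results are seen.

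**What to change.** In sections 9.1.1.4 and 9.7.3.1, split single-dose person-time for two-dose brands at a prespecified brand-specific analytical cut-off: the interval recorded for the brand plus a fixed grace period. Set both from the dose-interval description already planned in 9.3.1, before outcomes are analysed. Label the parts *one dose, within interval* and *dose 2 overdue*. Each person moves into the second part on the day the cut-off is passed without a recorded second dose, with no use of later information. Report VE for both and read one-dose VE from the first. State how the completion groups in 9.7.2 relate to these windows. This is a rule for dividing person-time only and leaves the vaccination schedule untouched.

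The cost is one extra time split in the existing data set, plus less person-time and a wider interval in the capped window. For illustration, take a 14-day grace period, a 21-day gap and 5% non-completion. The first 14 overdue days of non-completers sum to 1,015, so the capped window holds 495 + 0.05·1,015 = 545.75 of the 653 units, or 84%. Time beyond the dose interval falls from 24.2% to 50.75/545.75 = 9.3% of the window. A shorter grace period lowers that share further and costs more person-time.

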#### **9.7.3.2 Adjustment for Confounding**

Backward stepwise selection method will be used to identify variables associated with each outcomes according to a level of significance ( $p\text{-exit} \geq 0.1$ ,  $p\text{-entry} < 0.05$ ) for inclusion or exclusion, that could confound the effectiveness estimates and thus adjust the final models.

Confounders will be measured at baseline and updated before each vaccine dose is administrated or every 28 days (in order to update the collection of confounders during the follow-up of both, vaccinated and unvaccinated patients). The adjusted vaccine effectiveness for all the outcomes will be estimated as 1 minus the adjusted HR.

Adjusted time-specific RDs (e.g., RD at 3, 6, 9, 12 months after time zero) will also be tested [38]

Patients receiving one type of vaccine who receive later a dose of another COVID-19 vaccine, will be considered switcher from the date that the last dose was received and analysed as switchers, since such censoring/switch can be informative. Among switchers, each combination of vaccines will be analysed separately.

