### **9.3.4 Covariate Assessment**

In order to control for measurable confounders in the analysis, the following variables will be collected: lifestyle characteristics (BMI, smoking alcohol use), comorbidities, comedICATIONS, and health care utilisation prior to or at time zero and updated every 21 days and at every change in the exposure period (i.e. when receiving D1, D2) at the patient level. Given that risk factors for COVID-19 infection are not currently well understood [30], we will measure covariates that are classically controlled for in pharmacoepidemiologic research and leaves room for the inclusion of risk factors yet to be determined.

As explained in [Data source](#), clinical events will be collected by using the International Classification of Primary Care (ICPC) and the International Classification of Diseases 9th Revision (ICD-9) medical terms (6,7).

The following variables will all be assessed as last status before time zero:

- Smoking status
- Body mass index
- Alcohol use

The following comorbidities (and others that may be shown to be associated with COVID-19 prognosis) will be assessed ever before time zero and updated:

- Diabetes mellitus (types 1 and 2)
- Hypertension record
- Cardiovascular disease
- Cerebrovascular disease
- Chronic respiratory disease
- Chronic kidney disease
- Chronic liver disease
- Cancer

- Immunodeficiencies including Human immunodeficiency virus and other immunosuppressing conditions
- Autoimmune disorders

Comedication use will be assessed through pharmacy dispensing and primary care physician prescribing records by ATC. Considered comedications may be indicative of comorbidities placing patients at higher risk or markers of health care-seeking behaviour and utilisation and may serve as markers of patients' history of other infections or be risk factors for severe COVID-19 disease themselves. The following comedications will be assessed during the year before time zero and updated:

- Antibiotics
- Antiviral medications
- Corticosteroids
- Non-steroidal anti-inflammatory drugs
- Other Analgesic
- Psychotropics
- Statins
- Immunosuppressant medication use

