Health care utilisation in the year before time zero and updated will be evaluated as measures of health care-seeking behaviour, overall health status, and access to health care. Additionally, short-term health care utilisation in the 2 weeks before and including time zero and updated will be recorded separately, as short-term markers of current health status may influence individuals' vaccination decisions. Considered variables will include the following:

- Primary care utilisation (number of visits to PC)
- Influenza vaccination (number in the previous 5 years)
- Other vaccinations (number in the previous 5 years)
- COVID-19 tests (total number)

Frailty has been demonstrated as a confounder of vaccine-outcome associations in older adults [5,6,9]. Additional personal characteristics demonstrated to be associated with frailty [6,31,32] should be included as confounding factors, and may include the following:

[figure not shown]
- Wheelchair use
- Home hospital bed
- Paralysis
- Parkinson's disease
- Skin ulcer

- Weakness
- Stroke/brain injury
- Ambulance transport
- Dementia
- Difficulty walking
- Home oxygen
- Rehabilitation care
- Psychiatric illness
- Sepsis
- Heart failure
- Podiatric care
- Bladder continence
- Diabetes complications
- Arthritis
- Coagulation deficiencies
- Vertigo
- Lipid abnormalities

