\*Data storage and quality assurance will be performed according to the BIFAP governance that can

be consulted in the website of BIFAP.

Section 12: Limitations	Yes	No	N/A	Section Number
12.1 Does the protocol discuss the impact on the study results of:				
12.1.1 Selection bias?				9.9 ¶
12.1.2 Information bias?				9.9*
12.1.3 Residual/unmeasured confounding? (e.g. anticipated direction and magnitude of such biases, validation sub-study, use of validation and external data, analytical methods).				9.9 ‡
12.2 Does the protocol discuss study feasibility? (e.g. study size, anticipated exposure uptake, duration of follow-up in a cohort study, patient recruitment, precision of the estimates)				9.5

Comments:

¶Selective recruitment into the study of vaccinated/unvaccinated subjects from those recorded in the database with quality criteria (up-to-standard information) that are not representative of the general vaccinated/unvaccinated subjects respectively in the source population could produce selection bias. Some examples are described in the protocol '9.9 Limitations of the Research Methods' section.

\* If vaccinated individuals had less likelihood of screening or test than unvaccinated (due to a feeling of induced immunoprotection among vaccinated), we would artificially observe more cases among unvaccinated, directing toward a biased higher vaccine effectiveness estimation. The opposite could also be true, i.e. if vaccinated individuals had more likelihood of screening because they have a health/test-seeking behaviour, we would artificially observe more cases among vaccinated, directing toward a biased lower vaccine effectiveness estimation.

‡No information about the job and type of residence will be available. Consequently, confusion may still be present due to the higher probability of infection among them versus other social groups. That aspect would direct towards a reduction in the effectiveness estimations.

Section 13: Ethical/data protection issues	Yes	No	N/A	Section Number

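### The adjusted VE may condition on covariates changed by vaccination and may lose real confounders where events are few; the covariate update interval is also stated two ways

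*Protocol*

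**What the plan says.** The comparative model is Cox regression, and the adjusted VE is 1 minus the adjusted HR (Protocol 9.7.3.1 and 9.7.3.2). Section 9.7.3.2 fixes two rules for the adjustment.

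- **Selection.** "Backward stepwise selection method will be used to identify variables associated with each outcomes according to a level of significance", with exit at p of 0.1 or more and entry below 0.05. It names no variable that must stay. Section 9.7.5 adds a second data-driven rule: incompletely recorded variables such as BMI or smoking are removed if they show little confounding.
- **Timing.** "Confounders will be measured at baseline and updated before each vaccine dose is administrated or every 28 days", for vaccinated and unvaccinated people alike.

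Section 9.3.4 lists the candidates. Health care use covers primary-care visits and the number of COVID-19 tests, and "short-term health care utilisation in the 2 weeks before and including time zero and updated will be recorded separately". Comedication, including analgesics, antibiotics and corticosteroids, is assessed over the year before time zero and is also updated. The timing there is "prior to or at time zero and updated every 21 days and at every change in the exposure period".

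Annex 1 (ENCePP checklist, comments to Section 12) accepts that vaccination may alter testing. It begins "If vaccinated individuals had less likelihood of screening or test than unvaccinated (due to a feeling of induced immunoprotection among vaccinated" and concludes that VE would be biased upward; it adds that the opposite could also occur.

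Birth year, sex, region and time zero are matched (9.1.1.5 and 9.3.1), so they do not depend on selection.

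**The concern.** Section 9.1.1.4 rightly says that covariate assessment should be aligned with time zero. Section 9.7.3.2 then lets covariates run on after vaccination. A test count, a recent visit or an analgesic prescription recorded after the first dose may be a consequence of that dose. It also comes before an outcome that is itself a positive test. Ordinary Cox adjustment for such a variable can remove part of the vaccine effect, open a non-causal path, or partly correct unequal testing. The plan does not say which of these is intended, and it provides no method for covariates affected by earlier exposure.

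The selection rule is a separate weakness. Association with the outcome at a p-value threshold is not a test for confounding, and its power depends on the number of events. Adjustment sets may therefore differ between outcomes, and they may be thinnest where data are sparse, such as hospitalisation or death. The protocol (section 7) regards confounding as probably the main threat to validity, and every adjusted VE passes through these rules.

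**Working it through.** **1. The plan's own figure.** Section 9.7.3.2 states none. The nearest is the probability of 1 in Table 1. First row at 1:1: each arm has 7,720,843 / 2 = 3,860,421 people and the unexposed risk is 0.0006057.
- Unexposed events: 3,860,421 × 0.0006057 ≈ 2,338. Exposed events: 2,338 × 0.05 ≈ 117. Total ≈ 2,455.
- SE(log RR) ≈ sqrt(1/117 + 1/2,338) = 0.095. P = Φ((2.996 − 1.96 × 0.095)/0.095) = 1.000.

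The figure reproduces and is not affected by this point.

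**2. Chance that a real confounder survives selection.** Assumed: HR 1.5, prevalence p = 20%, D events in the model, retention at p < 0.10 (the exit threshold). Approximation: SE = 1/sqrt(D·p·(1−p)) and P(kept) = Φ(ln 1.5/SE − 1.645) + Φ(−ln 1.5/SE − 1.645). Example with D = 100: SE = 1/sqrt(16) = 0.25, 0.405/0.25 = 1.62, P = 0.49.

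| Events | Kept |
|---|---|
| 25 | 21% |
| 50 | 31% |
| 100 | 49% |
| 200 | 74% |
| 500 | 98% |
| 1,000 or more | about 100% |

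The documents give no event rate for hospitalisation or death, so these counts are a range and not a forecast.

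**3. Cost of losing it.** Assumed prevalence 30% in vaccinated and 20% in unvaccinated: the HR is multiplied by (1 + 0.3 × 0.5)/(1 + 0.2 × 0.5) = 1.15/1.10 = 1.045. A VE of 70% becomes 1 − 0.30 × 1.045 = 68.6%. This is for one confounder.

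**4. Direction when a post-vaccination variable is in the model.** If the variable has hazard ratio h and prevalence p0 (unvaccinated) and p1 (vaccinated), conditional RR = RR × (1 + (h−1)p0)/(1 + (h−1)p1). Take RR 0.331 (VE 66.9%, Table 1, Janssen) and assumed h and prevalences:
- h = 3, p0 = 20%, p1 = 10%: 0.331 × 1.4/1.2 = 0.386, VE 61.4%.
- h = 5, p0 = 10%, p1 = 20%: 0.331 × 1.4/1.8 = 0.257, VE 74.3%.

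The sign depends on inputs that the documents do not give.

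**5. Updated test count, simulated.** Assumed: 1.5 million people, half vaccinated; six 28-day intervals; infection risk 1% per interval if unvaccinated; VE against infection 70%; testing propensity varying between people; detection rising with testing; testing multiplied by a factor after vaccination. Piecewise Poisson fits approximate the Cox model (SE of log HR 0.012 to 0.016).

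| Testing factor | VE without updated count | VE with updated count |
|---|---|---|
| 0.5 | 80.5% | 79.0% |
| 0.7 | 75.4% | 74.4% |
| 1.0 | 69.3% | 69.4% |
| 1.5 | 63.0% | 65.0% |

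The shift is 0 to 2 points, toward 70%. Visits and comedication were not simulated, so this does not bound the whole problem.

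**6. Overlap with the outcome definition.** Symptomatic infection needs symptoms recorded in primary care within 14 days of the sample (9.3.3.2). When an update falls less than 14 days before the sample, the 2-week utilisation variable covers part of that window. If samples are spread evenly between updates, this happens for 14/28 = 50% of samples under one interval and 14/21 = 67% under the other. The visit that makes a case symptomatic can then also be a covariate.

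**7. Interval.** Section 9.3.4: every 21 days and at each exposure change. Section 9.7.3.2: before each dose or every 28 days. Both cannot be carried out.

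**The case against.** **The variables are only candidates.** A reader might infer that every model is over-adjusted. The documents do not support that: vaccination must change the variable, and the variable must survive selection in that model. Where vaccination leaves testing unchanged, the simulation shows no shift.

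**Adjusting for testing may help.** If vaccinated people simply test more or less, that is detection bias, which section 9.9 names, and the updated count partly corrects it. This stands. The 74.3% example above is partly such a correction and should not be read as pure harm. It is a reason to report that model deliberately as a sensitivity analysis.

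**The primary comparison has many events.** A reader might take the 117 exposed-arm events of Table 1 as the relevant count. With HR 1.5 and prevalence 10%, SE = 1/sqrt(117 × 0.09) = 0.308 and the confounder would be dropped 63% of the time. But precision depends on total events. With 2,455, SE = 0.067, z = 6.0, and the chance of dropping it is below 1 in 100,000. The selection problem belongs to sparse models.

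**Some updating is legitimate.** Comparators "may be vaccinated later during their follow-up period and then contribute to the vaccinated group", and values measured before their own first dose are pre-exposure. Values measured before dose 2 precede that dose and may predict whether and when it is given. This stands, and freezing everything at dose 1 has a cost.

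**Other mitigations.** Crude VE is also reported. BMI, smoking and alcohol are listed as last status before time zero. Section 9.3.4 says that frailty markers should be included. However, 9.7.3.2 makes no exception for them, and no text exempts tests or visits or stops updating at the first dose.

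**Conclusion.** The point holds in limited form. As written, the adjusted model may condition on variables that vaccination changes and that precede or partly define the outcome. The documents do not allow a direction or size to be assigned. For the test count alone, a simulation on assumed inputs gives 0 to 2 VE points.

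Selection by outcome p-value may give different adjustment sets for different outcomes and lose real confounders where events are few: about 21% retention at 25 events and 49% at 100, against essentially 100% at 1,000 or more, for an assumed HR of 1.5 and prevalence of 20%. Losing that one confounder would move a VE of 70% to about 68.6% under the assumed imbalance. Matched birth year, sex, region and calendar time are unaffected, and so is Table 1.

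Selection repeated by brand or by time window is a further possible inference, but 9.7.3.2 speaks only of outcomes. The 21-day versus 28-day conflict is a plain contradiction and needs no assumption.

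**What to change.** - Delete the stepwise rule in 9.7.3.2. Choose one confounder set from 9.3.4 on subject-matter grounds and force it into every model. Bring the removal rule in 9.7.5 into line.
- In the primary model, use covariates measured at each person's time zero, reset when a comparator is vaccinated. Leave out test counts, visits and comedication recorded after vaccination.
- Use updated values, including those taken before dose 2, only through a method suited to covariates affected by prior exposure, such as weighting.
- Report a model with the updated test count as a sensitivity analysis for detection bias.
- State one update interval in 9.3.4 and 9.7.3.2.

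The cost is mainly wording, with some extra programming if weighting is used. Confidence intervals will be slightly wider in rare-outcome models. Without weighting, there is less control of health changes between doses.
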